### 6.5.1.2. Component Analysis

The annualized rate of porphyria attacks is a composite endpoint including three components: 1) attacks requiring hospitalization; 2) attacks requiring urgent healthcare visit; or 3) attacks requiring IV hemin administration at home. The AAR of each of the three components will be analyzed using the same negative binomial regression model and the estimated ratio of mean AARs between treatment arms with corresponding 95% confidence interval will be provided. Zero-inflated negative binomial regression model will also be used to analyze each component to address the potential issue of an “excessive” number of patients with zero attack. When there are less than 10 patients experiencing attacks in a component, model-based analysis will not be conducted for that component.

### 6.5.1.3. Analysis in the Per Protocol Set

The analysis of the primary endpoint using negative binomial regression model will also be conducted for the Per Protocol Set (PPS) (defined in Section 4 ).

### 6.5.1.4. Sensitivity Analysis

The attack data collection is on calendar days, i.e. start and stop times by hours are not collected. To evaluate the impact of potential under- or over-counting of attacks due to the 1-day window, the following two sensitivity analyses will be performed for attacks meeting the primary endpoint definition:

- Count all discrete attacks even if they overlap during a day.
- Extend the attack counting windows to a 2-day window, i.e. attacks that occurs on the same calendar day, or are separated by one calendar day will be counted as one attack.

An Andersen-Gill model using the same fixed effects as the primary model will be performed treating the attacks as recurrent events.

If the number of zero attacks are high, a zero inflated negative binomial model will be performed to provide further assurance of the results.

Attack data could be missing if a patient stops attack data collection before the end of the 6m-DB period, e.g. due to study discontinuation. The missing data period is defined as the time (days) between the end of attack data collection and Day 162 which is the earliest expected end of the 6m-DB period of a patient, inclusive. For patients who provide attack data through the end of 6m-DB period, no missing data imputation will be performed. If  $\geq 5\%$  patients on givosiran arm have missing attack data, a pattern mixture model (PMM) with MI will be performed to assess the robustness of primary analysis results to the possible violation of the MAR missingness assumption. The details of the PMM approach for attack data is described in Section 9.4 .

In addition, AAR based on the following revised definitions will also be analyzed using the primary analysis method:

- All investigator-confirmed attacks: all attacks meeting the protocol defined criteria, including attacks requiring hospitalization, urgent healthcare visit, IV hemin administration at home, or treated at home not requiring hemin use.

- Potential attacks: in addition to the investigator-confirmed attacks, attacks not confirmed by investigator but were deemed as potential attacks will also be included. Attacks that were reported due to entry errors will be excluded. An Alnylam medical monitor reviewed the reasons that investigators decided a reported attack was not a protocol-defined attack to determine which could be considered potential attacks (e.g., exclusion of unique potential attacks due to duplicate or accidental entry). This was done in a blinded manner prior to the 6m-DB period interim database lock and unblinding.

For these analyses, attacks with duplicated or overlapping dates will be counted as one attack.

### 6.5.2. Secondary Endpoints

The annualized-event-rate type of endpoints include the annualized rate of hemin administration in AIP patients ( $FAS_{AIP}$ ) and the AAR requiring hospitalization, urgent care visits or IV hemin treatment at home in AHP patients (FAS) over the 6m-DB period. The number of events for each patient is annualized in the same way as AAR defined for the primary endpoint, divided by treatment period (in days) and multiplied by a year (365.25 days). These endpoints will be analyzed using a negative binomial regression model similar as the one used for the primary endpoint. Since hemin is administered as a one dose per day regimen, the annualized rate of hemin administration will be evaluated by the annualized days of hemin use.

The biomarker endpoints include the ALA levels in AIP patients ( $FAS_{AIP}$ ) at 3 months and 6 months, the urinary PBG levels in AIP patients ( $FAS_{AIP}$ ) at 6 months. Any postbaseline ALA/PBG values measured within 3 days after hemin use during the 6m-DB period will be treated as missing and excluded from analysis. For each biomarker secondary endpoint, the biomarker levels at the specified time point will be estimated and compared between two treatment arms using an MMRM model. The model will include baseline of the corresponding biomarker level as a continuous covariate, stratification factors (prior hemin prophylaxis status and historical attack rates), visit, treatment, and visit by treatment as fixed effects, and patient as a random effect. An unstructured covariance matrix will be used to model the within-subject error. If the fit of the unstructured covariance structure fails to converge, a compound symmetry covariance structure will be used. The least squares (LS) means and the corresponding SEM and 95% CIs for each treatment arm, along with the LS mean difference between two treatment arms at each post-baseline visit will be presented. The p-value for the treatment difference for each endpoint (ALA at Month 3 and Month 6; PBG at Month 6) will be presented. In addition, the overall p values measuring the average treatment effect on ALA and PBG during the entire 6m-DB period will also be reported to assess the durability of the treatment effect. If normal assumptions are violated, a non-parametric Wilcoxon rank sum test will be performed. For ALA at Month 3 and Month 6, if the drop-out rate during the 6m-DB period is  $\geq 5\%$  on the givosiran arm, sensitivity analyses will be performed using a PMM approach as described in Section 9.3.

Daily worst scores for pain measured by BPI-SF in Numeric Rating Scale (NRS), fatigue measured by BFI-SF in NRS, and nausea measured by NRS are collected through eDiary. For each of the symptoms (pain, fatigue and nausea), daily eDiary entries will be averaged into a weekly (i.e. 7 day) score. The change from baseline in weekly mean scores is defined as the post-baseline weekly mean score minus the baseline score. The AUC of change from baseline over 6 months in the respective measure will be calculated for each patient based on change from

baseline in weekly mean scores. For each of the measures, the AUC of change from baseline will be compared between two treatment arms using ANCOVA model with fixed effects of treatment arms and two stratification factors. In addition, the average weekly score change from baseline over 6 months will also be calculated and analyzed using ANCOVA.

Symptoms are expected to be elevated during porphyria attacks. This AUC approach encapsulates the peaks of these symptoms during attacks as well as lingering chronicity of these symptoms throughout the entire treatment period. AUC approaches have been used in other episodic conditions to compare both the severity and duration of pain across groups.

The weekly mean score will be calculated using the following algorithm:

1. A completed week will be defined as a week where a patient completes 4 or more daily entries in a week, which is consistent with other diary-based PRO research. The available eDiary entries for a completed week will be averaged to determine the weekly symptom score.
2. A missing week will be defined as a week where a patient is missing 4 or more daily entries. In a missing week, if there is one or more recorded attack days during the week, the mean score will be derived based on the following rules:
  - If there are 1 or more completed attack day diary entries, the mean weekly score will be computed as an average of the daily entries for that week.
  - If there is no completed attack day diary entry, the weekly mean score will be imputed using the average of all non-missing attack-week weekly mean scores within the same treatment period for the patient. If there's no non-missing attack week score, the weekly mean score will be imputed by the worst weekly mean scores within the same treatment period for the patient.

Patients are expected to have elevated symptom scores during porphyria attacks, which can span over multiple days. This algorithm intends to preserve any completed eDiary entries collected during days associated with attacks.

3. In a missing week without any attack days, the weekly mean score will be imputed by the last observed non-missing week without any attack days. If there is no last observed non-missing week without any attack days, the imputation will be based on baseline observation carried forward (BOCF).

The SF-12 scores are obtained using the Optum (PRO CoRE 1.3 Smart Measurement® System) software with the 2009 U.S. general population t-scores applied. For the Physical Component Summary (PCS) of SF-12 score, change from baseline at Month 6 in AIP patients (FASAIP) will be analyzed using an MMRM model with baseline score as a continuous covariate, fixed effect terms including treatment arms, stratification factors, visit (Month 3 or Month 6), and visit by treatment interaction.

All secondary endpoints defined for the AIP patients will also be analyzed for the AHP patients using similar methods.

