## 5.7. Multiple Comparisons/Multiplicity

At the time of the unblinded interim analysis, only the first secondary efficacy endpoint ALA levels at Month 3 will be assessed. A significance level of 0.001 will be used when comparing the ALA levels between the two treatment arms using an ANCOVA model.

For the final analyses of the 6m-DB primary treatment period, a significance level of 0.049 will be used to test the efficacy endpoints, reflecting a penalty of 0.001 for the unblinded interim analysis. A fixed-sequence testing strategy for the primary and secondary endpoints will be implemented to control the overall type I error rate. The primary endpoint will be compared between treatment arms at the significance level of 0.049. If the test is statistically significant, then the secondary endpoints will each be tested at the same significance level of 0.049 in the order specified in the efficacy endpoint section (Section 3.2 ). If the test of an endpoint in the sequence is not statistically significant, the testing of remaining endpoints in the sequence will stop and the null hypotheses for the subsequent tests will not be rejected.

There will be no multiplicity adjustment for exploratory endpoints.

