### 6.5.1. Primary Endpoint

The primary endpoint of the study is the annualized rate of porphyria attacks requiring hospitalization, urgent healthcare visit, or IV hemin administration at home in patients with AIP over the initial 6m-DB period. The primary analysis set for the primary endpoint is  $FAS_{AIP}$  (defined in Section 4).

The number of qualifying porphyria attacks is annualized for each patient using below formula:

$$\text{Annualized attack rate (AAR)} = \frac{\text{total number of porphyria attacks}}{\text{total number of days in the treatment period}} \times 365.25.$$

Let  $\lambda_G$  represent the mean AAR for givosiran arm and  $\lambda_O$  represent the mean AAR for the placebo arm. The hypotheses of the primary analysis are:

$$H_0: \frac{\lambda_G}{\lambda_O} = 1 \quad H_A: \frac{\lambda_G}{\lambda_O} \neq 1$$

The statistical significance level for the primary analysis of the primary endpoint is 2-sided 0.049. An estimated AAR ratio :  $\frac{\lambda_G}{\lambda_O} < 1$  and 2-sided p-value  $< 0.049$  will lead to rejection of  $H_0$ .

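### The confirmatory ALA/PBG MMRM carries a redundant patient random effect, and its only fallback, compound symmetry, may not protect the Month 6 type I error

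*SAP*

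**What the plan says.** SAP 6.5.2 compares ALA at Months 3 and 6 and PBG at Month 6 between arms by MMRM. After the baseline covariate and the fixed effects, the model has "patient as a random effect. An unstructured covariance matrix will be used to model the within-subject error". One fallback is named: "If the fit of the unstructured covariance structure fails to converge, a compound symmetry covariance structure will be used". The section gives no intermediate structure, no empirical (sandwich) standard error and no denominator-df method. Kenward-Roger appears only in the SAS code for the interim ANCOVA (SAP 9.2). The distributional back-up is separate: "If normal assumptions are violated, a non-parametric Wilcoxon rank sum test will be performed".

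These are confirmatory tests. Under SAP 5.7, "the secondary endpoints will each be tested at the same significance level of 0.049 in the order specified in the efficacy endpoint section". ALA at Month 6 and PBG at Month 6 are the second and third secondary endpoints (SAP 3.2.2), so they are the third and fourth tests once the primary is counted.

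The MMRM in Protocol 8.2.5.2 lists the baseline covariate and fixed effects only. SAP 9.1.3.3 repeats the random-factor wording and the same fallback for the interim durability model.

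**The concern.** A random patient effect adds one constant to every element of the within-patient covariance matrix. An unstructured matrix can already absorb any such constant, so the likelihood is flat in one direction. Compound symmetry already contains a common patient component, so the redundancy remains in the fallback.

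The practical risk is a chain. The over-specified model may fail to converge because of how it is written, not because of the data. The SAP then sends the confirmatory test to compound symmetry, which assumes one variance and one correlation from Week 2 to Month 6. If the true Month 6 residual variance is above the average over visits, the pooled variance understates the Month 6 standard error. A gatekept test would then run above its level, its 95% interval would be too narrow, and a false rejection would open the later tests in the sequence.

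**Working it through.** **Inputs from the documents.** Seven post-baseline visits (Week 2, Months 1 to 6; SAP Table 1). About 70 AIP patients randomized 1:1, so 35 per arm (SAP 5.1, 2.2). Two-sided level 0.049 (SAP 5.7, 6.5.1), so z = 1.9686. Month 3 ALA mean (SD) 20.0 (11.1) on placebo and 2.3 (1.1) on givosiran (SAP, power paragraph before 9.1.3).

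**The plan's own figure.** The only operating characteristic given for ALA is more than 90% power with 40 patients at 0.001. Pooled SD = √((11.1² + 1.1²)/2) = 7.89; SE = 7.89 × √(2/20) = 2.49; 17.7/2.49 = 7.10; 7.10 − 3.29 = 3.81, so power is 99.99% (99.7% by Welch t). The figure is reproduced. No error rate or convergence figure is given for the MMRM.

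**Redundancy.** An unstructured 7 × 7 matrix has 7 × 8/2 = 28 parameters. Adding a patient variance makes 29, but the map to the marginal matrix has rank 28. Patient variance plus compound symmetry has 3 parameters and rank 2. In both cases the marginal matrix, and with it the treatment estimate, SE and p-value, is still determined.

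**Month 6 error under compound symmetry.** Let R be the Month 6 residual variance divided by the average over the 7 visits. With a model-based SE the rejection rate under the null is 2 × [1 − Φ(1.9686/√R)], and the interval width relative to the correct one is 1/√R. Simulated values come from 2,000 null trials per setting, 35 per arm:

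| R | Formula | Simulated |
|---|---|---|
| 0.5 | 0.005 | 0.007 |
| 0.67 | 0.016 | 0.020 |
| 1 | 0.049 | 0.054 |
| 1.25 | 0.078 | 0.076 |
| 1.5 | 0.108 | 0.109 |
| 2 | 0.164 | 0.145 |

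The R = 1 simulation used correlation decaying with time, so a wrong correlation alone does little harm; unequal variance drives the error. With 15% dropout the simulated error was 0.044 at R = 1 and 0.111 at R = 1.5. The unstructured fit without a random effect gave 0.043 to 0.060 in all complete-data settings.

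**What R might be.** The documents do not say, so the following is assumed: raw variance 1 at every visit, a fraction f of it independent visit noise, and a correlation of the remainder that decays by a factor ρ per month. The covariance of visit t with baseline is c_t = (1 − f)ρ^t. With one common baseline slope b = mean of c_t, the residual variance is 1 − 2b·c_t + b², and its average is 1 − b². Example, ρ = 0.90 and f = 0: b = 0.738 and c_6 = 0.531, so R = (1 − 0.784 + 0.545)/(1 − 0.545) = 1.67, and the error is 2 × [1 − Φ(1.524)] = 0.128.

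| Noise f | R (ρ = 0.80 / 0.90 / 0.95) | Month 6 error | Relative CI width |
|---|---|---|---|
| 0 | 1.45 / 1.67 / 1.80 | 10.2 / 12.8 / 14.3% | 0.83 / 0.77 / 0.745 |
| 20% | 1.25 / 1.30 / 1.26 | 7.8 / 8.4 / 7.9% | 0.89 / 0.88 / 0.89 |
| 40% | 1.13 / 1.14 / 1.10 | 6.4 / 6.5 / 6.1% | 0.94 / 0.94 / 0.95 |

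Simulation of the first row gave 0.102, 0.131 and 0.154; the second gave 0.072 to 0.084. At Month 3 the same formula with c_3 gives 4.9 to 5.6%, and simulation gave 0.047 to 0.060.

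**Effect on the ALA conclusion.** With 35 per arm and the Month 3 planning figures, z = 17.7/(7.89 × √(2/35)) = 9.4. If the variance doubles, z = 9.4/√2 = 6.6.

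**The case against.** Four points on the other side carry weight.

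- **The wording may be loose.** Patient as a random effect may simply mean patient as the subject of the repeated-measures matrix. The protocol's MMRM and the SF-12 MMRM in SAP 6.5.2 name no random effect. If so, this half of the point is a clarification. It is still needed, because a programmer following the text would fit both terms.
- **The fallback is conditional.** It applies only if the unstructured fit fails to converge. The SAP does not say whether a Hessian warning counts, and there is no estimate here of how often the fallback would be used.
- **The direction of the error is not in the documents.** ALA SDs are given at Month 3 only. Baseline adjustment with decaying correlation makes R above 1 the natural expectation, but that is an assumption. The 10-14% figure also needs zero visit noise, which is hard to square with creatinine-normalised spot urine and with the SAP's own remark on variability in PD measures (SAP 7.1). The 20% and 40% rows are more moderate, though they too are assumed.
- **ALA is very likely safe.** The planning effect is large enough that no value of R considered here would reverse it.

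A reader might infer that the non-identifiable variance invalidates the confirmatory test, or that compound symmetry always inflates it. Neither follows: the marginal covariance is identified, and the test is conservative when R is below 1. Nor does the Month 6 argument reach SAP 9.1.3.3. That model averages over Months 1 to 3, and the interim test at 0.001 is an ANCOVA with multiple imputation.

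What stands is the redundant term, the single fallback, and the absence of a robust SE or df rule. The Wilcoxon back-up addresses non-normality, not covariance.

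**Conclusion.** The point holds as a conditional weakness. The SAP text is over-parameterised by one, both in the main model and in the fallback, and a resulting convergence failure would move confirmatory Month 6 tests to a structure that may not hold their level. Against the nominal 4.9%, the Month 6 error under compound symmetry would be about 10-14%, 8% or 6-6.5% with 0, 20% or 40% visit noise, with intervals about 5-25% too narrow. These sizes assume normal residuals, equal variance in both arms under the null, and correlation with baseline decaying by a factor of 0.80 to 0.95 per month. If Month 6 residual variance is half to two-thirds of the visit average, the error falls to about 0.5-2%. Month 3 ALA is near nominal and the primary endpoint is unaffected. The ALA Month 6 conclusion is unlikely to change; the documents give no planning figures for PBG, so the same cannot be said there. Reported intervals would be affected whatever the significance.

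**What to change.** In SAP 6.5.2, delete the patient random effect, name patient as the subject of the unstructured repeated-measures matrix, and state Kenward-Roger degrees of freedom. Make the matching deletion in 9.1.3.3 for consistency only. Replace the single fallback with a pre-specified order that lets variance differ by visit, for example heterogeneous Toeplitz and then heterogeneous AR(1). Keep compound symmetry as a last step only, with empirical (sandwich) standard errors. State what counts as a failure to converge. Other heterogeneous sequences would also serve; the error rate of this one was not simulated.

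The cost is SAP wording. If the unstructured fit converges, the fallback changes have no effect. If a fallback is used, Month 6 intervals will be slightly wider.

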8.2.10. Interim Analysis

An unblinded interim analysis will be conducted when approximately 30 AIP patients have completed at least 3 months of the treatment period. The endpoint for this interim analysis is the ALA level at 3 months. The ALA level at 3 months will be compared between treatment arms using an ANCOVA model with fixed effect of treatment arms, stratification factors for AIP patients (prior hemin prophylaxis status and historical attack rates), and with baseline ALA as a

covariate. An alpha-spending function will be used to adjust the significance level to ensure the overall type I error rate is not inflated; the error spending function will be specified in the statistical analysis plan. The significance level for the comparison at the interim is 0.001 (2-sided). To assess durability of the study drug in lowering and maintaining ALA level over time, the overall treatment effect from Month 1 through Month 3 will be evaluated through a mixed effect model repeated measurement (MMRM).

Stopping for efficacy or futility is not planned in this study. To ensure that the study is adequately powered for the primary endpoint comparison at the final analysis, attack rates may also be evaluated in a blinded manner for sample size reassessment at the time of the interim analysis.

The interim analysis will be described in detail in the SAP.

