### **3.2.2. Secondary Endpoints**

- Urinary ALA levels in patients with AIP at 3 months
- Urinary ALA levels in patients with AIP at 6 months
- Urinary PBG levels in patients with AIP at 6 months

- Annualized rate of administered hemin doses (evaluated by annualized days of hemin use, see Section 6.5.2 for details) in patients with AIP over the 6m-DB period
- Annualized rate of porphyria attacks requiring hospitalization, urgent healthcare visit, or IV hemin administration at home in patients with any AHP over the 6m-DB period
- Daily worst pain score as measured by Brief Pain Inventory-Short Form (BPI-SF) numeric rating scale (NRS) in patients with AIP over the 6m-DB period
- Daily worst fatigue score as measured by Brief Fatigue Inventory-Short Form (BFI-SF) NRS in patients with AIP over the 6m-DB period
- Daily worst nausea score as measured by NRS in patients with AIP over the 6m-DB period
- Change from baseline in the Physical Component Summary (PCS) of the 12-item Short-Form Health Survey (SF-12) in patients with AIP at 6 months

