### 9.1.3.3. Durability of ALA Lowering

The primary ANCOVA model (without missing data imputation) will be applied to evaluate the treatment effect at Week 2, Month 1 and Month 2. The LS mean ALA levels over time will be plotted for each treatment arm to assess the longitudinal treatment effect of Givosiran on ALA lowering. Spaghetti plots for individual patient will also be provided.

In the givosiran-treated arm, it is expected that there will be substantial ALA knockdown starting at Month 1 and maintained throughout the treatment duration. To assess the durability of treatment effect in ALA knockdown, the overall treatment effect over 3 post-baseline visits Month 1, Month 2 and Month 3 will be evaluated through a mixed effect model repeated measurement (MMRM). The MMRM model includes baseline ALA level as a continuous fixed covariate, stratification factors (prior hemin prophylaxis status and historical attack rates), visit and treatment as fixed factors, and patient as a random factor. An unstructured covariance matrix will be used to model the within-subject error. If the fit of the unstructured covariance structure fails to converge, a compound symmetry covariance structure will be used. The overall LS mean treatment difference measuring the average treatment effect on ALA from Month 1 to 3 and associated p value will be estimated.

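### The p-value named as the assessment of ALA and PBG durability tests the effect averaged over visits, so it cannot show partial waning (minor)

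*SAP*

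**What the plan says.** Protocol 8.2.10 sets the question for the interim: "To assess durability of the study drug in lowering and maintaining ALA level over time, the overall treatment effect" over Months 1 to 3 is to be evaluated in an MMRM. SAP 9.1.3.3 carries this out: "The overall LS mean treatment difference measuring the average treatment effect on ALA from Month 1 to 3 and associated p value will be estimated". The interim model there lists baseline ALA, the stratification factors, visit and treatment, with patient as random. It lists no visit-by-treatment term.

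For the final analysis, SAP 6.5.2 states: "overall p values measuring the average treatment effect on ALA and PBG during the entire 6m-DB period will also be reported to assess the durability". The model there does contain the interaction: "visit, treatment, and visit by treatment as fixed effects, and patient as a random effect".

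The same paragraph of SAP 6.5.2 plans more than the overall p-value. The "LS mean difference between two treatment arms at each post-baseline visit will be presented", and "The p-value for the treatment difference for each endpoint (ALA at Month 3 and Month 6; PBG at Month 6) will be presented". Month 6 ALA is itself a listed secondary endpoint ("Urinary ALA levels in patients with AIP at 6 months", SAP 3.2.2) and is tested in the fixed sequence of SAP 5.7, where "a significance level of 0.049 will be used to test the efficacy endpoints".

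Neither document defines a durability criterion, such as a retained fraction or a late-minus-early contrast.

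**The concern.** Durability means that lowering, once achieved, is maintained. The analysis given that name has a different null hypothesis: a treatment difference of zero when averaged over visits. A large early effect rejects that null whatever happens later. The interim model goes further. With no visit-by-treatment term it fits one constant difference across Months 1, 2 and 3, so it assumes what durability should examine.

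What is at stake is the wording of a claim. If ALA lowering wanes to, say, half by Month 6, the overall p-value and the Month 6 p-value would both still be significant. A report could then call the effect durable on the strength of the p-value that the SAP names for that purpose.

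**Working it through.** **Inputs from the documents.** Month 3 ALA mean (SD): placebo 20.0 (11.1), givosiran 2.3 (1.1) mmol/mol, difference 17.7 (SAP 9.1.2). About 70 AIP patients randomised 1:1, so 35 per arm (SAP 5.1, 2.2). Final alpha 0.049, taken as two-sided as stated for the primary endpoint (SAP 5.7, 6.5.1). Seven post-baseline visits, Week 2 and Months 1 to 6 (Protocol Table 1).

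**Assumptions not in the documents.** Compound-symmetric within-patient correlation ρ of 0.3 to 0.8; givosiran SD between 1.1 and 11.1; the waning patterns below; no missing data; no precision gain from the baseline covariate.

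**The plan's own figure.** SAP 9.1.2 states more than 90% power for Month 3 ALA with 40 patients at 0.001. With SD 11.1 in both arms, 17.7 / (11.1 × √(2/20)) = 5.04, and noncentral t gives 91.7%. With the root-mean-square SD of 7.89 it gives 99.9%. The figure is reproduced. The documents state no operating characteristic for the durability p-value.

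**Overall p-value at the final analysis.** The standard error of the visit-averaged difference is SD × √((1+6ρ)/7) × √(2/35). With SD 11.1 in both arms, which is conservative, this is 1.68 at ρ = 0.3 and 2.42 at ρ = 0.8. The critical value is about 2.00.

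| True pattern | Average difference | Ratio to SE (ρ 0.3 / 0.8) | Significant (ρ 0.3 / 0.8) |
|---|---|---|---|
| Sustained | 17.7 | 10.5 / 7.3 | 100% / 100% |
| Wanes to half by Month 6 | 17.7 × 5.5/7 = 13.91 | 8.3 / 5.8 | 100% / 100% |
| Absent at Months 4–6 | 17.7 × 4/7 = 10.11 | 6.0 / 4.2 | 100% / 98% |
| Lost after Month 1 | 17.7 × 2/7 = 5.06 | 3.0 / 2.1 | 84% / 54% |

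The half row covers both a straight line from Month 1 to half at Month 6 and a step to half at Month 4, because the retained fractions sum to 5.5 in each. Simulation with the smaller givosiran SD leaves the first three rows at about 100% and raises the last to as much as 98%. The sustained and half rows cannot be told apart.

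**Month 6 test under the same patterns.** When the effect is gone at Month 6, the test is significant in about 5% of simulated trials, so it exposes total loss. When the effect is halved, 8.85 / (11.1 × √(2/35)) = 3.3, which is significant in about 91% of trials, and in more with a smaller givosiran SD. It does not expose halving.

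**Interim.** I simulated the model without the interaction, with unstructured covariance, 20 per arm and a 0.049 threshold used for illustration. With the effect present at Months 1 and 2 and absent at Month 3, the overall p-value is significant in about 82–100% of trials. The lower end has SD 11.1 in both arms.

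**Late-minus-early contrast.** For the change in treatment difference from Month 1 to Month 6, the standard error is SD × √(2(1−ρ)) × √(2/35). With SD 11.1 in both arms this is 3.14 at ρ = 0.3 and 1.68 at ρ = 0.8.
- Full at Month 1, half at Month 6: 8.85/3.14 = 2.8 and 8.85/1.68 = 5.3, giving 79% and over 99%.
- Waning already under way from Week 2, so that 11/12 remains at Month 1: the change is 17.7 × 5/12 = 7.38. At ρ = 0.3, 7.38/3.14 = 2.35, or about 63–64%.

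Across patterns, SDs and correlations, the contrast detects a halving in about 63–100% of trials.

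**The case against.** The overall p-value is supplementary. It is added after the by-visit results, lies outside the fixed sequence, and has no alpha, success criterion or decision role. The rest of SAP 6.5.2 already gives a reader most of what is needed: an interaction model, a treatment difference at every visit, and Month 3 and Month 6 tests. At the interim, SAP 9.1.3.3 also applies ANCOVA at Week 2, Month 1 and Month 2 and plots LS mean and individual ALA over time, and SAP 9.1.3.1 tests Month 3 at 0.001. Waning under continued monthly dosing is also hypothetical. SAP 9.1.2 reports a plateau from Day 21 held for three months, though in only three treated patients.

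Most of this stands, and it rules out several stronger readings that a reader might infer:
- *Complete loss could go unnoticed.* It could not: the Month 6 ALA and PBG tests and the by-visit differences would show it, as would the Month 3 test and earlier ANCOVAs at the interim.
- *The p-value is nearly always significant whatever happens.* This depends on when the effect is lost and how large it is. The figure is 54–98% for loss after Month 1, and 50–84% for an effect half as large and lost after Month 3 (SD 11.1, ρ 0.3 to 0.9).
- *The same figures apply to PBG.* The documents give no PBG mean or SD.
- *The p-value is meant to carry a formal claim.* The Amendment 3 summary lists durability analyses among its purposes, but no section gives this p-value a decision role.

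The objection does not remove the mismatch. The only p-value labelled as durability does not address durability, and the by-visit results are tied to no stated criterion.

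**Conclusion.** The point holds as a minor one. The analysis named for durability tests an average effect. At the SAP's ALA effect size it gives essentially the same answer whether the effect is sustained or halves by Month 6, and it is significant in about 98–100% of trials even when nothing remains at Months 4 to 6. The interim model also imposes a constant effect. The harm not covered elsewhere is a durability statement when the effect has waned only partly.

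The primary endpoint, the secondary endpoints and type I error control are untouched. The percentages rest on the assumed correlation, givosiran SD, waning patterns and complete data. They apply to ALA only.

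**What to change.** 1. In SAP 6.5.2, SAP 9.1.3.3 and Protocol 8.2.10, describe the overall p-value as the average treatment effect over the period, not as an assessment of durability.
2. Add visit-by-treatment to the interim MMRM in SAP 9.1.3.3, matching SAP 6.5.2.
3. State that durability is assessed from the by-visit treatment differences with 95% CIs, together with one prespecified contrast: the change in treatment difference from Month 1 to the last visit (Month 6 at the final analysis, Month 3 at the interim), with its 95% CI.

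A rule that every monthly visit must be significant should not be the criterion. At the final analysis it passes a halved effect in about 77–99% of simulated trials.

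The cost is wording, one added model term and one contrast per biomarker. No new data, patients or alpha are needed. The downside is slightly more reporting and a less favourable durability statement if the interval is wide. That is more likely at the interim. With 20 per arm, SD 11.1 and ρ = 0.3, the contrast's standard error is 11.1 × √1.4 × √(2/20) = 4.15, so a halving of 8.85 is only 2.1 standard errors.
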